9.2.2 Assessment of secondary outcomes

Docking time and operation time, as well as conversion rate (into laparoscopic or open surgery), will be reported after the operation in the CRF.

The length of hospital stay will be reported at the discharge of the patient in the CRF and include the day of admission to the hospital and including the day of discharge from the hospital. Re-admission rate will be reported at the 30-days follow-up.

9.2.3 Assessment of other outcomes of interest

See Chapter 5.2

9.2.4 Assessment of safety outcomes

See Chapter 5.1

9.2.4.1 Adverse events

Any adverse event during the operation or until 30 days after the operation will be reported with its time of onset, duration, resolution, action to be taken, assessment of intensity, and relationship with the medical device. After the operation and during its hospital stay, each patient will be visited at least one time a day from the surgical resident. Vital signs, laboratory parameters, and clinical evaluation will help us to identify adverse events and treat them appropriately. During the postoperative control at 30 days postoperative, the surgeon will perform an anamnesis and clinical evaluation of the patient to identify adverse events. If required, further examination such as laboratory parameters, vital signs measurement, or diagnostic (CT-Scan, Gastroscopy, Reoperation) may be requested by the surgeon. Laboratory measurement will be performed by the laboratory of the Inselspital.

The most common complications after bariatric surgery are: anastomotic or staple line leakage, postoperative bleeding, pulmonary complications, thromboembolic complications and surgical site infection.

9.2.4.2 Laboratory parameters

A pregnancy test (urine sample) will be performed on the day of the operation upon arrival at the hospital (see Chapter 9.3.2).

At days 1 and 2, after the operation, a blood sample is performed to measure the blood count, CRP, kidney value, sodium, and potassium.

More tests are effectuated according to the clinic of the participant.

These blood tests correspond to the standard performed in laparoscopic bariatric surgery and no additional blood tests are planned in robotic bariatric surgery.

9.2.4.3 Vital signs

Vital signs will be taken when the participant arrives in its room on the day of the operation. During the induction phase, the operation and the waking phase, the participant is monitored (ECG, Blood pressure, oxygen saturation, heart rate) under the surveillance of an anaesthesiologist and a nurse anesthetist. When the participant is stable, he will be transferred to the regular station. Vital signs will be measured three times a day until its release from the hospital. If indicated, vital signs will be measured during the postoperative consultation at 30 days.

This surveillance corresponds to the standard performed in laparoscopic bariatric surgery and no additional surveillance are planned in robotic bariatric surgery.

9.2.5 Assessments in subjects who prematurely stop the clinical investigation

If the bariatric operation was already performed, the follow-up would be performed as usually done in our bariatric center (with clinical control at 1, 3, 6, and 12 months during the first year, then each 6 to 12 months during the following years). The clinicopathological data and outcome will be collected for safety reasons but will not be included in the study.

If the bariatric operation has not yet been performed, but the patient still wants to benefit from the bariatric procedure, and if there is no contraindication, this one will be performed with the usual laparoscopic technic and the follow-up will be performed as usually done in our bariatric center. The clinical data collected will be used for the study up to the point of withdrawal only.

If the bariatric operation has not yet been performed and the patient does not wish to benefit from it or if the procedure is contraindicated, he will be redirected to a conservative weight loss program according to the situation. The clinical data collected will be used for the study up to the point of withdrawal only.

The number of patients who prematurely stop the study will be reported.

9.2.6 Follow-up of the subjects after the regular termination of the clinical investigation

As in laparoscopic bariatric surgery, patients are checked after the 3-month follow-up, in a standard way at 3, 6, 12 and 18 months after the operation and then annually with a blood test and a clinical check-up. This follow-up will be done in a similar way for patients who have had robotic bariatric surgery.

9.3 Procedures at each visit

9.3.1 Peroperative consultation

All patients where bariatric surgery is indicated and desired are seen at this consultation to plan the operation. During this visit, and for those who meet the inclusion criteria, the possibility of participating in the study will be discussed. The patient will receive oral and written information about the study. If the patient meets the inclusion criteria for the study and is willing to participate, he will be included.

The operation will be planned and explained to the patient. A consultation with the anesthesiologist will be organized.

9.3.2 Operation and Hospital stay 3-4 days

Day 0:

Pregnancy test (urine)
Exclusion and Inclusion criteria will be tested
Operation

Hospital stay of 3-4 days.

After the operation and during its hospital stay, each patient will be visited at least once a day from the surgical resident. Vital signs, laboratory parameters, and clinical evaluation will help us to identify adverse events and treat them appropriately. If required, further examination such as laboratory parameters, vital sign measurements, or diagnostic (CT-Scan, Gastroscopy, Reoperation) may be requested by the surgeon.

9.3.3 Postoperative consultation (30 day after the operation)

During the postoperative control at 30 days postoperative, the surgeon performs an anamnesis and

clinical evaluation of the patient to identify adverse events. If required, further examination such as laboratory parameters, vital sign measurements, or diagnostic (CT-Scan, Gastroscopy, Reoperation) may be requested by the surgeon.

10. SAFETY

10.1 Definition and Assessment of (Serious) Adverse Events and other safety related events

Adverse Event (AE) (Art. 2 Abs 57 MDR)

Any untoward medical occurrence, unintended disease or injury or any untoward clinical signs (including an abnormal laboratory finding) in subjects, users or other persons whether or not related to the MD.

Serious Adverse Event (SAE) (Art. 2 Abs 58 MDR)

Any adverse event that led to any of the following:

- (a) death,
- (b) serious deterioration in the health of the subject that resulted in any of the following:
 - (i) life-threatening illness or injury,
 - (ii) permanent impairment of a body structure or a body function,
 - (iii) hospitalisation or prolongation of patient hospitalisation,
 - (iv) medical or surgical intervention to prevent life-threatening illness or injury or permanent impairment to a body structure or a body function,
 - (v) chronic disease,
- (c) foetal distress, foetal death or a congenital physical or mental impairment or birth defect.

Note: planned hospitalization for pre-existing condition, or a procedure required by the CIP, without a serious deterioration of the health status of the subject, is not considered an SAE

Device deficiency (Art. 2 Abs 59 MDR)

Inadequacy of a medical device related to its identity, quality, durability, reliability, safety or performance, of an investigational device, including malfunction, user errors and inadequate information supplied by the manufacturer.

Malfunction (ISO14155)

Failure of an investigational device to perform in accordance with its intended purpose when used in accordance with the instructions for use or the CIP.

Device deficiency with Serious Adverse Device Effect (SADE) potential (Art. 80 Abs 1 letter c MDR; ISO14155)

Any device deficiency that might have led to a serious adverse event if appropriate action had not been taken, intervention had not occurred, or circumstances had been less fortunate.

Adverse Device Effect (ADE) (ISO14155)

Adverse event possibly, probably or causally related to the use of an investigational device or procedures.

Serious Adverse Device Effect (SADE) (ISO14155)

Adverse device effect (ADE) that has resulted in any of the consequences characteristic of a serious adverse event.

Unanticipated Serious Adverse Device Effect (USADE) (ISO14155)

Serious adverse device effect (SADE) which by its nature, incidence, severity or outcome has not been identified in the current version of the risk analysis report.

Causal Relationship of SAE (MDCG 2020-10/1)

A causal relationship towards the medical device or the procedure of the investigation should be rated

by the Co-Investigators and the Sponsor-Investigator as follows:

- **Not related:** The relationship to the device or procedures can be excluded.
- **Possible:** The relationship with the use of the investigational device is weak but cannot be ruled out completely. Alternative causes are also possible.
- **Probable:** The relationship with the use of the investigational device seems relevant and/or the event cannot reasonably be explained by another cause.
- **Causal relationship:** The serious event is associated with the investigational device or with procedures beyond reasonable doubt.

10.2 Adverse events categorization

The adverse events are categorized by the PI and the Sponsor using the following algorithm:

Does the AE meet the seriousness criteria?

- No, it is not serious
 - Is the relationship to the device or the procedure possible, probable or causal?
 - No: non-related AE
 - Yes: ADE
- Yes, it is serious: SAE
 - Is the relationship to the device or the procedure possible, probable or causal?
 - No: non-related SAE
 - Yes: SADE
- Is it anticipated (within expected type, severity and frequency of the complications)?
 - No: unanticipated SADE (USADE)
 - Yes: anticipated SADE (ASADE)

10.3 Documentation and reporting in Medical Device Category C clinical investigations

Not applicable

10.4 Documentation and reporting in Medical Device Category A clinical investigations

Device deficiencies (DD) and all **adverse events (AE)** including all **serious adverse events (SAE)** are collected, fully investigated and documented in the source document and appropriate case report form (CRF) during the entire investigation period, i.e. from patient's informed consent until the last CIP-specific procedure, including a safety follow-up period.

- Documentation of AEs (including SAEs) by the Co-Investigators includes diagnosis or symptoms, start and stop dates of event, event treatment, event resolution, assessment of seriousness and causal relationship to MD and/or investigation procedure (Art. 32 ClinO-MD, ISO14155).
- Documentation of DDs by the Co-Investigator includes description of event, start date, investigational device information, action taken with regard to the investigational device, and whether the DD led to an AE. The Sponsor-Investigator shall review all DDs and determine and document in writing whether they could have led to a SAE (DD with SADE potential) (Art 32. ClinO-MD, ISO14155).

Information on AEs is systematically collected during the hospitalization after the operation (2-3 days) and at the regular study visits 30-days after to the procedure, as applicable and clinically justified in the context of the specific protocol. In case of premature study withdrawal of a participant after the operation, he will still benefit of a 30-days visit as it is the case for all patients after bariatric surgery in our center.

10.4.1 Foreseeable adverse events and anticipated adverse device effects

Possible adverse effects specific to the Senhance™ Surgical System are the same as traditional laparoscopic surgery. Due to a learning curve, the operation time will probably be, in the beginning,

longer than in general laparoscopic bariatric surgery.

Mortality at less than 30 days after a Sleeve Gastrectomy is estimated at 0.29% (95% CI : 0.11 to 0.63%) and for Roux-en-Y gastric bypass at 0.38% (95% CI: 0.22-0.59%). The reoperation rate after a Sleeve Gastrectomy is estimated at 2.96% and for Roux-en-Y gastric bypass at 5.34%. The postoperative complication rate after a Sleeve Gastrectomy is estimated at 8.9% and for Roux-en-Y gastric bypass at 12.0%. [23]

The most common complications after bariatric surgery and their treatments are:

- anastomotic or staple line leakage → endoscopic or surgical closure / drainage
- postoperative bleeding → blood transfusion, coagulation optimization, reoperation
- pulmonary complications → antibiotics, invasive ventilation
- thromboembolic complications → anticoagulation
- surgical site infection → local treatment, VAC therapy, antibiotics

We expect no adverse events specifically related to Senhance™ Surgical system. Expected possible adverse events are the same as in traditional laparoscopic bariatric surgery. For other robotic platforms, literature reports a similar rate of postoperative morbidity and mortality between robotic and laparoscopic bariatric surgery [9, 24].

10.4.2 Reporting of Safety related events

Reporting to the Sponsor:

All SAEs, device deficiencies and health hazards that require measures are reported to the Sponsor-Investigator by the Co-Investigators (or authorized designee) within 24 hours after becoming aware of the event. Device deficiencies are assessed regarding their potential to lead to an SAE. DD are assessed regarding their potential to lead to an SAE.

Pregnancies

On the day of the operation each female participant that can be pregnant (except hysterectomy, postmenopausal) will have a pregnancy test. If the test is positive, the operation will be reported and the participant excluded from the study.

Reporting of pregnancies after the operation is not necessary.

Reporting to the Competent Ethics Committee:

The Sponsor-Investigator reports to the CEC promptly any serious adverse event which has a causal relation with the MD, comparator or procedure/test method or where a causal relation appears to be possible (Art. 33 ClinO-MD).

In order to ensure prompt notification, the Sponsor-Investigator may initially submit an incomplete notification.

If safety and health hazards that require measures must be taken immediately during the conduct of the investigation, the Sponsor notifies the CEC within 2 days of these measures and the circumstances which made them necessary (Art. 34 ClinO-MD).

Periodic safety reporting (Art. 35 ClinO-MD):

An Annual Safety Report (ASR) is submitted by the Sponsor-Investigator to the CEC, yearly. The ASR contains a list of all SADEs and DDs and a report on their degree of seriousness, causal relationship with the MD and procedure and on subjects' safety.

Other reporting is done according to provisions of MD vigilance as per Art. 87-90 MDR (Art. 33 abs 4.b ClinO-MD) and Art. 67 MedDO.

10.5 Assessment, notification and reporting on the use of radiation sources

Not applicable

11. STATISTICAL METHODS

11.1 Hypothesis

The investigator's hypothesis is that, robotic in bariatric is a safe and efficient way to perform bariatric surgery.

11.2 Determination of Sample Size

The study is designed as single arm, two-stage phase II study with a stopping rule for safety using the Simon's two-stage design.

Literature shows a complication rate for conventional laparoscopic bariatric surgery of 10%. We expect to have similar complication rates with bariatric surgery. For calculation of the safety stopping point we set the maximum acceptable threshold of complications at 25%.

We used Simon's 2 stage design to derive the time point of an interim analysis and a stopping rule for safety, assuming Type I error to be 0.05 and Type II error 0.8.

Simon's optimal two-stage design yielded the following numbers with respect to a 25% threshold:

- Interim analysis will be done at 22 patients. If there are 5 or more events, the study will stop for safety.
- Final analysis will be done at 39 patients. Robotic surgery can be regarded as successful if less than 6 events occurred.

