Statistical considerations:	The primary endpoint of our study is the safety of this new robotic platform in bariatric surgery. Therefore our study is designed as a single arm, two-stage phase II study with a stopping rule for safety using the Simon's two-stage design. Considering that conventional laparoscopic bariatric procedures present a complication rate around 10%, we set the maximum acceptable threshold of complication at 25%. Type I error is assumed to be 0.05 and Type II error 0.8. Therefore a sample size of 39 patients is needed with an interim analysis at 22 patients. The stopping rule is 5 or more events at the interim analysis and robotic surgery is considered safe if less than 6 events occurred. Baseline characteristics and perioperative data will be presented as medians (IQ-range) for continuous variables or frequencies (percentages) for categorical variables. For statistical analysis SPSS Version 25 will be used. The docking time and operation time will be represented as a visual graphic with its evolution over time.
Compliance statement:	This investigation will be conducted in compliance with the CIP, the current version of the Declaration of Helsinki, ISO14155, ICH-GCP (as far as applicable) as well as all national legal and regulatory requirements.

ABBREVIATIONS

Provide a list of abbreviations used in the CIP – to be completed/adapted

AE Adverse Event

ADE	Adverse Device Effect
ASA score	American Society of Anesthesiology
ASADE	Anticipated Serious Adverse Device Effect
ASR	Annual Safety Report
BMI	Body mass index
CA	Competent Authority (e.g. Swissmedic)
CEC	Competent Ethics Committee
CIP	Clinical investigation plan
ClinO	Ordinance on Clinical Trials in Human Research (in German KlinV, in French Oclin, in Italian OSRUM)
ClinO-MD	Ordinance on Clinical Trials with Medical Devices (in German: KlinV-Mep, in French: Oclin-Dim, in Italian: OSRUM-Dmed)
CRF	Case Report Form (pCRF paper CRF; eCRF electronic CRF)
DD	Device Deficiency
DMC / DSMC	Data Monitoring Committee, Data Safety Monitoring Committee
Ho	Null hypothesis
H1	Alternative hypothesis
HRA	Federal Act on Research involving Human Beings (in German: HFG, in French: LRH, in Italian: LRUm)
IB	Investigator's Brochure
ICF	Informed Consent Form
ICH-GCP	International Council for Harmonisation – guidelines of Good Clinical Practice
IFU	Instruction For Use
ISF	Investigator Site File
ISO	International Organisation for Standardisation
ITT	Intention to treat

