3.5 Justification for the design of the clinical investigation

Robotic surgery presents the advantage of better visualization with high definition, more ergonomics, and facilitates some complex laparoscopic tasks such as suturing [3, 4]. These advantages are especially relevant in bariatric surgery where abdominal obesity is often a cause of uncomfortable and

tedious position for the surgeon and restrains the exposure of the surgical field.

Our study will evaluate the feasibility and safety of Senhance™ Surgical System in bariatric surgery at a single center. Until now, this robotic system has not been investigated in bariatric surgery. The first step is to evaluate its feasibility and safety. Therefore, we propose a prospective pilot study during the introduction of this robot in our clinic. The aim initially is to analyze the feasibility and safety of this robot with a limited number of patients and this in a limited time to be able to highlight, if this new technology does not represent a risk for the patient in comparison to a conventional laparoscopic surgery. Therefore we plan to perform a prospective open observational single-center study with the advantage of less bias and confounding factors than in a retrospective study. To achieve a reasonable number of participants and to minimize selection bias we plan to offer robotic operation to all eligible patients. In view of the lack of data on this robot in bariatric surgery, a power analysis is not feasible. However, we have opted for a Simon's two stage design and thus perform an interim analysis with a stopping rule.

A randomized controlled trial with conventional laparoscopic is not yet feasible as we have to evaluate the feasibility and safety of this procedure first, as we recently introduced it in our centre. However subsequently and according to the results of this first study, a randomized study with a larger number of patients will be necessary to evaluate more precisely its outcome compared to bariatric surgery by conventional laparoscopy.

We started to operate with this new robotic platform on the 28.06.2021. On the planned starting date of the trial (01.12.2021) we expect still to be in the learning curve.

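### The stated type II error of 0.8 should be 0.2 (power 80%), and the 22/39 plan labelled Simon's optimal design is the minimax design

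*Protocol*

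**What the plan says.** Section 11.2 of the Protocol sets up a single-arm Simon two-stage design. It takes a complication rate of 10% from the literature on conventional laparoscopic bariatric surgery and sets 25% as the highest acceptable rate. The error rates are given as "assuming Type I error to be 0.05 and Type II error 0.8". The section then reports that "Simon's optimal two-stage design yielded the following numbers with respect to a 25% threshold": an interim look at 22 patients with a stop at 5 or more events, and a final analysis at 39 patients with success declared at fewer than 6 events.

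The synopsis (Statistical considerations) gives the same limits and repeats the error rates: "Type I error is assumed to be 0.05 and Type II error 0.8". It refers to Simon's two-stage design without the word optimal.

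Section 3.5 says that, for lack of data on this robot in bariatric surgery, "a power analysis is not feasible". The next sentence says that a Simon two-stage design was chosen instead.

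The Protocol nowhere states a power of 80% or a type II error of 0.2, and it does not mention the minimax design.

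**The concern.** The type II error is the chance of failing a platform whose true complication rate is the expected 10%. At 0.8, the trial would reject a safe platform four times in five. No investigator would plan for that, and it does not fit a sample of 39.

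For a Simon design the word optimal has a fixed meaning: among all designs that meet the error limits, it has the smallest expected sample size when the true rate is the unacceptable one. The minimax design has the smallest maximum sample size. The two usually differ, and an interim look at 22 of 39 looks late for an optimal design.

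This design is the only statistical basis for the sample size, the timing of the interim look, the safety stop in section 11.4.4 and the final success call. An ethics committee member or journal reviewer who enters the stated inputs into standard software will not get 22/39, and may conclude that the limits are wrong when they are not.

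**Working it through.** **Inputs** (section 11.2): unacceptable complication rate 25%; expected rate 10%; type I error at most 0.05; stop at ≥5 events in the first 22; success at ≤5 events in 39.

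**Formula.** Let X1 be the number of events in the first n1 patients and X2 the number in the remaining n − n1. With stopping limit s and success limit a, at true rate p:

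- P(success) = Σ over x = 0 … s−1 of P(X1 = x) × P(X2 ≤ a − x)
- P(early stop) = P(X1 ≥ s)
- Expected N = n1 + (1 − P(early stop)) × (n − n1)

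Type I error is P(success) at p = 0.25. Power is P(success) at p = 0.10.

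**Step 1: the Protocol's rule** (n1 = 22, s = 5, n = 39, a = 5; 17 patients in stage 2).

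| Events in first 22 | P at 25% | P(X2 ≤ 5−x) at 25% | Product | P at 10% | P(X2 ≤ 5−x) at 10% | Product |
|---|---|---|---|---|---|---|
| 0 | 0.0018 | 0.7653 | 0.0014 | 0.0985 | 0.9953 | 0.0980 |
| 1 | 0.0131 | 0.5739 | 0.0075 | 0.2407 | 0.9779 | 0.2354 |
| 2 | 0.0458 | 0.3530 | 0.0162 | 0.2808 | 0.9174 | 0.2576 |
| 3 | 0.1017 | 0.1637 | 0.0167 | 0.2080 | 0.7618 | 0.1585 |
| 4 | 0.1611 | 0.0501 | 0.0081 | 0.1098 | 0.4818 | 0.0529 |
| **Sum** | | | **0.0498** | | | **0.8024** |

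(Sums use unrounded terms.) Type I error is 0.0498 and power 0.8024, so the type II error is 1 − 0.8024 = 0.198. The probability of an early stop at a 25% rate is 0.677, and expected N = 22 + (1 − 0.677) × 17 = 27.5.

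**Step 2: type II error 0.8 taken literally.** With type I error ≤ 0.05 and power ≥ 0.20, the search gives 4 then 11 patients as both the optimal and the minimax design: stop at ≥1 event in 4, success only with 0 in 11. Check: 0.75^11 = 0.042 and 0.90^11 = 0.314. The stated input therefore does not lead to 22/39.

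**Step 3: which Simon design is 22/39?** All two-stage designs with type I error ≤ 0.05 and power ≥ 0.80 were enumerated, with N up to 75.

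| | Protocol | True optimal |
|---|---|---|
| n1, then N | 22, then 39 | 13, then 48 |
| Stop at | ≥5/22 | ≥3/13 |
| Success at | ≤5/39 | ≤7/48 |
| Type I error | 0.0498 | 0.0475 |
| Power | 0.802 | 0.809 |
| Early stop at 25% | 0.677 | 0.667 |
| Expected N at 25% | 27.5 | 24.6 |

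No design with N below 39 meets the limits. Among those with N = 39, 22/39 has the smallest expected N (27.50; the next is 23/39 with 27.53). It is therefore exactly the minimax design. It is not optimal: 13/48 has a smaller expected N, and so do others, such as 20/43 with 25.2.

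**Step 4: could other inputs rescue the label?** No. Reversing the hypotheses (10% as null, 25% as alternative) gives 18/43 as optimal and 22/40 as minimax. Type I error 0.025 gives 20/58 as optimal, and power 0.90 gives 23/63.

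**The case against.** The best reply is that nothing operative is wrong. The type I error, the 25% threshold, both sample sizes and both limits fit together, and 0.8 is plainly the power entered under the wrong name. The rule as it will be run fails a safe platform about 20% of the time, not 80%. That is right, and it is why this is a correction of wording and not of the design. It does not excuse the text: the error appears in two places and nothing in the Protocol corrects it.

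A second reply is that the Protocol never argues from a small expected sample size and uses the word optimal only once. That is also true. But the word is a technical term that identifies a specific design, and it identifies the wrong one.

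A third is that section 3.5 can be read as saying that no data specific to this robot existed, so a threshold design based on laparoscopic rates was used. The next sentence there supports this reading. It softens the inconsistency without removing it, because a Simon design cannot be derived without an alternative rate and a type II error. This is the least important part of the point.

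Finally, the attained values hold only if exactly 22 and then 39 patients are evaluable and each counts at most once. Section 11.5 does not replace drop-outs, and sections 11.2 and 11.4.4 count events. Attained values are conventionally quoted at the planned sample size, but the corrected text should say so.

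**Conclusion.** The concern holds. The type II error is misstated as 0.8 where the rule attains 0.198 (power 80.2%), and a minimax design is labelled optimal. Compared with the true optimal design, the Protocol's plan exposes on average 27.5 − 24.6 = 2.9 more patients if the true rate is 25%, and takes its first look at 22 patients instead of 13. In return its maximum is 39 patients instead of 48. That is a legitimate choice, but not the one the text names.

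The trial does not in fact have 20% power, and 39 patients and both limits are right for type I error 0.05 and power 80%. These figures assume independent patients, one yes/no outcome per patient, and full evaluability at 22 and 39. The text should be corrected because the sample size and the safety stop cannot be verified from it as it stands.

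**What to change.** In section 11.2 and in the synopsis, replace the description with wording such as: Simon's minimax two-stage design; unacceptable complication rate 25%, expected rate 10%; type I error 0.05 (attained 0.0498) and type II error 0.20 (attained 0.198, power 80.2%), with attained values calculated for 22 and 39 evaluable patients, each counted once.

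In section 3.5, delete the statement that a power analysis is not feasible, or limit it to saying that no data specific to this robot were available, so that rates from laparoscopic surgery were used.

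The sponsor should confirm that 22/39 is the design intended. If so, the cost is wording only, with no change to the sample size, the interim timing or the limits. If the optimal design was really meant, its sample sizes and limits differ (13 then 48), and the change would no longer be editorial.

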2.9 Early termination of the investigation

The Sponsor-Investigator may terminate the investigation prematurely according to certain circumstances, for example:

- ethical concerns,
- insufficient subject recruitment,
- when the safety of the subjects is doubtful or at risk, respectively,
- alterations in accepted clinical practice that make the continuation of the investigation unwise,
- early evidence of benefit or harm of the experimental intervention.

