7.4 Criteria for withdrawal / discontinuation of subjects

Participants can, at any time of the study and for any reason, withdraw their informed consent in verbal or written form. This withdrawal will lead to participant's exclusion from the study.

Study or routine procedures will be stopped if safety concerns are raised.

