11.4.4 Interim analyses

To guarantee the procedure's safety, the intraoperative and postoperative complications, as well as the postoperative mortality, will be analyzed after inclusion of 22 participant and will be presented as frequencies (percentages). The analysis will be done by the Sponsor-Investigator. If there are 5 or more events, the Sponsor-Investigator will terminate the study for safety.

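### The 5-event safety limit is applied only at the 22-patient look, although a fifth affected patient before then already makes the planned stop certain

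*Protocol*

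**What the plan says.** The 5-event limit appears in three places, each time attached to one look.

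- Synopsis, statistical considerations: "The stopping rule is 5 or more events at the interim analysis".
- Section 11.2, for the analysis at 22 patients: "If there are 5 or more events, the study will stop for safety".
- Section 11.4.4: complications and mortality "will be analyzed after inclusion of 22 participant and will be presented as frequencies (percentages"), and then "If there are 5 or more events, the Sponsor-Investigator will terminate the study for safety".

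Section 11.3, on statistical termination criteria, only refers back to 11.2. At 39 patients, section 11.2 calls the procedure successful if fewer than 6 events occurred; it attaches no stop to that second limit.

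Two general provisions could lead to an earlier stop. Section 2.9 lets the Sponsor-Investigator terminate "when the safety of the subjects is doubtful or at risk, respectively". Section 7.4, repeated in 6.3, states: "Study or routine procedures will be stopped if safety concerns are raised". Neither gives a count. Section 1.6 records that there is no data safety monitoring committee, and under 11.4.4 the Sponsor-Investigator carries out the interim analysis.

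**The concern.** The counted event here is harm to a patient, and reaching five is a mandatory stop. Once five of the first *k* patients (*k* < 22) are affected, the result at 22 is settled, and patients *k*+1 to 22 cannot change it. The plan's only numerical rule still lets those operations go ahead.

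Whether to stop sooner is then left to judgement, without a threshold and without an independent committee. Section 3.5 says the system has not been investigated in bariatric surgery and that the team expects still to be in its learning curve. At stake is the number of patients operated on after the sponsor's own stop has become certain.

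**Working it through.** **Inputs (section 11.2).** Acceptable rate 10%, unacceptable rate 25%, *n*₁ = 22 with a stop at 5 or more, *N* = 39 with success at 5 or fewer. The error rates are given as "assuming Type I error to be 0.05 and Type II error 0.8". The second figure works only as power 0.80, and is read that way here.

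**Step 1: reproduce the design.** With *X*₁ ~ Bin(22, *p*) and *X*₂ ~ Bin(17, *p*),

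P(declared safe) = Σₓ₌₀..₄ P(*X*₁ = x) · P(*X*₂ ≤ 5 − x).

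- *p* = 0.25: 0.0018·0.7653 + 0.0131·0.5739 + 0.0458·0.3530 + 0.1017·0.1637 + 0.1611·0.0501 = 0.0498.
- *p* = 0.10: 0.0985·0.9953 + 0.2407·0.9779 + 0.2808·0.9174 + 0.2080·0.7618 + 0.1098·0.4818 = 0.8024.

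The limits therefore meet 0.05 and 0.80.

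**Step 2: when the stop becomes certain.** Let *K* be the number in sequence of the fifth affected patient, so P(*K* = k) = C(k−1, 4) p⁵ (1−p)^(k−5). The stage 1 stop is the event *K* ≤ 22. At *p* = 0.25:

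- P(*K* ≤ 22) = 0.6765.
- P(*K* ≤ 15) = 0.31, P(*K* ≤ 18) = 0.48, P(*K* ≤ 21) = 0.63.
- Given a stage 1 stop, the mean of *K* is 15.7. In 63% of stage 1 stops *K* is 17 or less, so at least five operations follow the deciding patient.

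**Step 3: expected number operated.**

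- As planned: 22 + 17 · P(*K* > 22). At 25%: 22 + 17 · 0.3235 = 27.50.
- With the limit applied when reached: Σₖ₌₅..₂₂ P(*K* = k) · min(22, k + *L*) + 39 · P(*K* > 22), where *L* is the number of patients operated before the deciding event is known.

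The 30-day window corresponds to about 3.2 patients if 39 are enrolled in 12 months (section 6.1). It is about 3.5 if enrolment takes 11 months so that follow-up ends within the synopsis's 12-month duration. Lags of 0, 3 and 5 cover the range. The baseline assumes recruitment pauses at 22 until outcomes are known, which the protocol does not state.

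| True rate | P(stage 1 stop) | As planned | *L* = 0 | *L* = 3 | *L* = 5 | Saving (*L* = 0 / 3 / 5) |
|---|---|---|---|---|---|---|
| 10% | 0.0621 | 37.94 | 37.71 | 37.84 | 37.89 | 0.24 / 0.11 / 0.06 |
| 20% | 0.4571 | 31.23 | 28.81 | 29.92 | 30.44 | 2.4 / 1.3 / 0.8 |
| 25% | 0.6765 | 27.50 | 23.25 | 25.00 | 25.91 | 4.25 / 2.5 / 1.6 |
| 30% | 0.8355 | 24.80 | 18.60 | 20.89 | 22.17 | 6.2 / 3.9 / 2.6 |

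**Step 4: effect on the decision.** Only trials with *K* ≤ 22 stop earlier, and all of them stop at 22 under the present rule. P(declared safe) is therefore identical with and without the change: 0.8024, 0.1757, 0.0498 and 0.0105 at 10%, 20%, 25% and 30%.

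**Step 5: why the counting unit matters.** Step 4 holds if each patient counts at most once, and the protocol does not say whether an event is a patient or a complication. Suppose complications were counted and a fraction *f* of affected patients had two (an assumption). P(declared safe) at a true 10% rate would then be 0.72, 0.65 or 0.58 for *f* = 10%, 20% or 30%, against 0.80.

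**The case against.** The strongest reply is that nothing here is an error. A single look after stage 1 is how a Simon design is normally run, and stopping as soon as the limit is reached is an optional refinement that changes no decision. Earlier stopping is also available: sections 6.3 and 7.4 are worded as obligations, section 2.9 names harm among the grounds for termination, and section 10.4.2 brings every serious adverse event to the Sponsor-Investigator within 24 hours. On this view a number is missing, not a mechanism.

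That is accurate, but the number is what counts. The general clauses neither require nor define a stop at five, and the sponsor has already chosen five as the stopping number.

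Four qualifications stand:

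- The saving of 4.25 needs every outcome known before the next operation, so the lagged figures are the realistic ones. At the 10% rate the protocol expects, the gain is negligible.
- The 24-hour route covers serious events. Non-serious complications reach the record on paper forms at discharge and day 30 (sections 5.1 and 12.1.1).
- Feasibility data are lost when the limit is hit: given a stage 1 stop at 25%, 6.3 of 22 patients on average with no lag, and 3.7 at a lag of 3.
- Certainty requires that an affected patient stays in the count. Sections 8.4 and 9.2.5 disagree on whether outcome data of operated patients who withdraw are included, and should be reconciled.

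**Conclusion.** The concern holds as a matter of design, not of calculation. The limits of 5 in 22 and 6 in 39 are right for the stated rates, but the first is applied later than it need be. As written, operations may continue after the plan's own mandatory safety stop is fixed.

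The cost falls where it matters most. At the 25% rate the sponsor set as the threshold, it is about 1.6 to 2.5 patients per trial on average with realistic reporting delay, and 4.25 at the extreme of no delay. These figures rest on independent patients with a constant rate, one event per patient, and a pause at 22. The point concerns stage 1 only: section 11.2 attaches no stop to the second limit, and later patients inform the feasibility outcomes. The change should be made, though the trial's conclusion does not depend on it.

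**What to change.** Keep both limits and both scheduled analyses, and add two statements to section 11.2, repeated in 11.4.4 and the synopsis:

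1. An event is a patient with at least one qualifying complication, counted once.
2. The number of such patients is tracked continuously during stage 1, and the existing stop applies as soon as the fifth is confirmed among the first 22.

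Leave stage 2 as it is. The first statement has to come first, because the unchanged operating characteristics depend on it.

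The drafting cost is small, and serious events already reach the Sponsor-Investigator promptly. The practical cost is keeping the tally current for non-serious complications as the discharge and day-30 forms arrive. After an early stop the raw complication rate is biased upwards, which the report should say, and somewhat fewer docking-time and operation-time data will be available.
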